## ii. II. CALCULATION OF THE REVISION RATE

Thus, the all-cause revision rate will be calculated as follows:

$$Taux = \frac{n}{N}$$

Where  $n$  is the number of patients who underwent revision surgery and  $N$  is the total number of patients included in HF.

Specific revision rates will be calculated using the following formula:

$$T_R = \frac{n_i}{N}$$

With:

- $n_i$ , the number of patients who required revision surgery for reason  $i$ ;
- $N$ , the sample size;

The confidence interval of each revision rate thus observed (one for each reason for revision) will also be calculated as mentioned above.

## iii. CALCULATION OF THE SURVIVAL RATE

The Kaplan-Meier analysis is based on the calculation of cumulative conditional probabilities. The survival rate will be calculated using the following formula:

$$S_{t(i)} = \prod_{t(i-1) < t(i)} S_{\frac{t(i)}{t(i-1)}} = \prod_{t(i-1) < t(i)} 1 - \frac{D_i}{N_i}$$

With:

- $S_{t(i)}$ , the probability of having the implant in place so far;  $t_{(i)}$
- $S_{\frac{t(i)}{t(i-1)}}$ , the probability of still having the implant in place knowing that the implant was in place at  $t_{(i-1)}$  to  $t_{(i)}$
- $D_i = 1 - N_{s(i)}$ , the number of subjects who required removal or change of implant, observed at the time;  $t_{(i)}$
- $N_{s(i)}$ , the number of subjects with their implant still in place at the time observed at the time;  $t_{(i)}$
- $N_i = N_{s(i-1)} - D_i - C_i$ , the number of subjects at risk of implant removal or change, observed at time;  $t_{(i)}$
- $C_i$ , the number of censored subjects (lost to follow-up, deceased, having left the study) observed between time and  $t_{(i-1)}$  to  $t_{(i)}$

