## 3. CI DESIGN RATIONALE

### A. EVALUATION OF THE RESULTS OF THE RELEVANT PRECLINICAL EVALUATION

#### PERFORMED TO JUSTIFY THE USE OF THE DEVICE ON HUMAN SUBJECTS

The clinical evaluation of the SAGITTA® EVL R rods and associated locking keys demonstrated their compliance with the essential requirements on safety, acceptability of the benefit/risk balance, clinical performance and acceptability of adverse events.

However, in consideration of the elements evaluated, a post-marketing clinical study is considered necessary in order to:

- Generate postoperative clinical data (state-of-the-art revision rate of 15.2% at 5 years / 20.8% at 10 years).
- To confirm the clinical benefits associated with the use of the rods and their performance.

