### iii. PRIMARY AND SECONDARY OUTCOMES

The outcomes presented below were chosen in accordance with the HF objectives presented in Chapter 5C.

- Primary outcome:

The medium-term survival rate (minimum 4 years postoperatively) is defined via the Kaplan-Meier analysis, for all patients who still have the stem in place at the follow-up considered. Each inflection point will correspond to revision surgery with removal or change of the stem, all causes of revision combined.

- Secondary outcomes:

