### B. DATA DESCRIPTION

Demographic **data** of the included population and surgery, as well as endpoints and safety data, will be presented descriptively:

- Discrete qualitative and quantitative data will be summarized by their number, percentages, and percent confidence interval for each modality;
- Continuous quantitative data will be summarized by their mean, standard deviation, mean confidence interval, median, minimum and maximum.

**Clinical data** will be analyzed before and after surgery at each follow-up visit (functional measures) when available, including in terms of HHS and SHO-12 functional score if available, calculating score changes between preoperative and follow-up states. The confidence interval of the observed differences will make it possible to quantify the improvement or deterioration of the clinical status.

**Radiological data** will be analyzed before and after surgery at the follow-up visit. X-rays will document possible cases of complications (causal link with the bone defect), and provide information in terms of osseointegration/bone reconstruction.

Failure and revision rates will be analyzed by a Kaplan-Meier survival curve, with any revision surgery with removal or change of the SAGITTA EVL-R rod and/or locking keys as the inflection point. If several causes are identified, specific survival rates can be calculated.

The safety data related to the medical device will be presented throughout the duration of the follow-up. The complications observed can be grouped according to the data describing them provided and their etiology.

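### The Kaplan-Meier symbol list in Protocol 7.C.iii removes each failure from its own risk set and gives an impossible expression for the failure count

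*Protocol*

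**What the plan says.** Section 7.C.iii introduces its formula with "The survival rate will be calculated using the following formula" and writes each conditional factor as 1 - D_i/N_i. The symbols are then defined one by one:

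- Survivors: "N_{s(i)}$ , the number of subjects with their implant still in place" at t(i).
- Failures: "D_i = 1 - N_{s(i)}$ , the number of subjects who required removal or change of implant" at t(i).
- Risk set: "N_i = N_{s(i-1)} - D_i - C_i$ , the number of subjects at risk of implant removal or change" at t(i).
- C_i: the subjects censored between t(i-1) and t(i).
- The conditional factor, in words: "the probability of still having the implant in place knowing that the implant was in place at" the preceding time.

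Section 6.A.iii makes this the primary outcome and says "Each inflection point will correspond to revision surgery with removal or change of the stem". The same section carries the definition over to the component and etiology curves. Section 7.B says "Failure and revision rates will be analyzed by a Kaplan-Meier survival curve", and the synopsis also names Kaplan-Meier. Only 7.C.iii states a risk set.

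**The concern.** Two lines of the list conflict with their own labels. The risk set at an event time must include the subjects who fail at that time, but the printed N_i subtracts them. D_i is described as a number of failures, but its expression subtracts a number of subjects from 1, so it is negative whenever more than one implant is still in place.

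This is the only stated rule for computing the sole primary outcome, and the subgroup curves inherit it. An analyst who follows it gets an impossible value. One who repairs only the obviously broken D_i line gets a curve that is too low. Section 7.K also requires departures from the statistical plan to be presented and justified, so a correct Kaplan-Meier run would formally be a departure from the printed formula.

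**Working it through.** The protocol gives no survival figure to reproduce, so the check covers the algebra first and then its size.

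**Risk set.** By the verbal definitions, those in place at t(i) are those in place at t(i-1), less the censored, less the failures:

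`N_s(i) = N_s(i-1) - C_i - D_i`

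The right-hand side is the printed N_i, so the printed N_i equals N_s(i). The list gives the conditional probability only in words. Written out, those words mean N_s(i) / (N_s(i-1) - C_i), which equals 1 - D_i/(N_s(i-1) - C_i). The denominator has to be N_s(i-1) - C_i.

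**D_i taken literally.** 120 in place, one failure, no censoring:

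- D_1 = 1 - 119 = -118
- N_1 = 120 - (-118) - 0 = 238
- factor = 1 + 118/238 = 1.496, which is not a probability.

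**D_i repaired, N_i as printed, one failure of 120.**

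- Correct: 1 - 1/120 = 0.99167
- Printed N_i: 1 - 1/119 = 0.99160

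**Whole curve.** Inputs: 120 stems (section 7.E) and 18 failures. The 18 is an assumption based on the "state-of-the-art revision rate of 15.2% at 5 years" in section 3.A (0.152 x 120 = 18.2). Event times are taken as distinct and uncensored; the protocol does not exclude ties.

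- Correct: 102/120 = 0.8500
- Printed N_i: the factors 118/119, 117/118, ..., 101/102 multiply to 101/119 = 0.8487
- In general: (n - D)/n - (n - D - 1)/(n - 1) = D/(n(n - 1)); here 18/(120 x 119) = 0.00126, or 0.13 points.

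For 6, 12, 18 and 25 failures of 120, the shortfall is 0.04, 0.08, 0.13 and 0.18 points.

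**With censoring.** Section 6.D.iii expects many deaths and losses but gives no rate. The simulation assumed 120 stems, implantation uniform over 2016-2018, visits January to May 2023, exponential revision times with 15.2% revised by 5 years, and 10,000 runs per setting.

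| Assumed loss or death by 5 years | Mean shortfall at 5 years (points) | 1.96 x SD of the correct estimate (points) |
|---|---|---|
| 0% | 0.13 | 6.5 |
| 20% | 0.15 | 6.9 |
| 40% | 0.18 | 7.5 |
| 60% | 0.22 | 8.4 |

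The simple binomial half-width agrees: 1.96 x sqrt(0.85 x 0.15/120) = 6.4 points. The bias is roughly 2 to 3% of the half-width.

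**Where it is larger.** If the 18 failures fall in five tied groups (6, 4, 3, 3, 2), the shortfall is 0.52 points. If all are tied at one time, it is 0.8500 - (1 - 18/102) = 0.8500 - 0.8235, or 2.65 points. Subgroup sizes are not given. A second simulation used censoring uniform over 4 to 7.4 years plus loss or death at 0, 4 or 8% per year. Its mean 5-year shortfall was 0.54 to 0.71 points for 30 subjects and 1.1 to 1.5 points for 15. If the last subjects at risk all fail, the printed N_i is 0 and the factor is undefined.

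**The case against.** The strongest objection is that the text may be damaged. It is a translation read by a program, and the wording around these symbols is visibly garbled in places. A lost subscript could turn D_(i-1) into D_i, and a misread character could explain the 1 in the D_i line. This cannot be excluded, so the finding applies to the text as shown and the source should be checked first. Still, the N_i line is a well-formed expression. Changing its subscript to i-1 would not rescue it either, because N_s(i-1) is already net of earlier failures.

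The second objection is that nothing practical follows. The protocol names Kaplan-Meier repeatedly, the factor 1 - D_i/N_i is right, and the verbal labels for D_i and N_i are the standard ones. Standard software would bypass both lines, and a survival above 1 would be noticed at once. Sections 7.D and 7.G confirm that there is no test and no success criterion. All of this stands and limits the grade to minor. It does not make the printed rule correct.

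**Conclusion.** The point holds as a minor correction. On the text as shown, both expressions contradict their own labels, and no other section supplies a correct risk set.

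Taken literally, the D_i line gives impossible values. With D_i read as the failure count, the printed N_i understates survival once any failure has occurred. On the main curve near 120 stems with few ties, the 5-year shortfall averages about 0.1 to 0.2 points against a half-width of 6 to 8 points. That rests on the assumed 15.2% revision rate, exponential times and assumed loss rates. The word small applies to that curve only: heavy ties or small component and etiology subgroups can bring the shortfall to between half a point and a few points.

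**What to change.** Check both lines against the source-language text. If they stand there as shown here, replace them with:

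- N_i = N_s(i-1) - C_i, those at risk just before t(i), including those who fail at t(i)
- D_i = number of subjects with removal or change at t(i)
- N_s(i) = N_i - D_i
- S(t) = product of (1 - D_i/N_i) over all event times up to t

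This changes a few lines of protocol text, with no cost to data or timeline.

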## D. DEGREES OF SIGNIFICANCE AND STRENGTH OF THE CI

The objectives of this CI are descriptive regarding the use of SAGITTA® EVL-R rods; Thus, no statistical test is performed to compare the results with a comparator device.

## **E. SAMPLE SIZE**

According to the available data, 120 SAGITTA® EVL R revision rods were implanted at the Rouen University Hospital – Charles Nicolle Hospital between 01/01/2016 and 31/12/2018. The final sample size will reflect the current practice of the selected investigation center based on the patient base as observed over the inclusion period and meeting the selection criteria.

The total sample size will depend on the number of subjects who do not object to participation and data collection, the number of subjects who have died and have been lost to follow-up.

## **F. LEARNING CURVE AND DATA CONSIDERATION**

No learning curve will be considered due to the retrospective nature (previously implanted subjects), the experience of the surgeon who implanted the patients, and the number of annual rod insertions in the selected investigation centers. All patients who meet the inclusion criteria and do not object to participation and data collection will be included.

## **G. HF PASS/FAIL CRITERIA**

The nature of HF is observational and its objectives are only descriptive, no statistical criterion defines the success or failure of the investigation.

## **H. INTERIM ANALYSES AND DISCONTINUATION OF CI FROM A STATISTICAL POINT OF VIEW**

### **i. INTERIM ANALYSES**

No interim analysis is envisaged because the prospective part of the study is limited to the patient's only and last follow-up visit.

### **ii. CESSATION OF HF BASED ON STATISTICAL CRITERIA**

The nature of HF is observational, ambispective, and since its objectives are only descriptive, there is no statistical criterion that defines its early termination.

## **I. ACCOUNTING FOR BIASES**

### **i. STATISTICAL BIAS**

The statistical biases usually limited by the use of a comparator arm with a randomized distribution for each arm and double-blind conduct cannot be implemented for this HF due to its ambispective non-interventional non-comparative and therefore non-randomized, open-label nature.

However, the subjects included in this study will constitute an ongoing and exhaustive series.

### **ii. CONFOUNDING FACTORS**

Medical and surgical history, as well as intercurrent pathologies, or any other factor such as age, weight, etc. and that may impact clinical outcomes will also be considered during multivariate analysis.

### **iii. SPECIFYING SUBGROUPS FOR ANALYSIS**

Subjects can optionally be classified by assembly for analysis.

In addition, an analysis according to etiology (revision, revision with reconstruction) is envisaged. For this purpose, the CCAM codes related to the surgical procedure will be recovered.

**iv. CHECKING AND ADJUSTING ERROR PROBABILITIES**

The purpose of this clinical investigation is to describe current practice, with descriptive objectives for the use of SAGITTA EVL-R rods; Thus, no statistical tests or adjustments to these tests are performed.

**J. HANDLING MISSING, UNUSED OR ERRONEOUS DATA, INCLUDING ABANDONMENTS AND WITHDRAWALS**

**i. DATA INCLUSION METHODOLOGY**

The simple imputation replacement method can be used if necessary: replace the missing data with a plausible value (mean/median of the variable for the follow-up under consideration, for example) if less than 10% of the data are missing..

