#### **Functional Clinical Scores and Ratings**

- *Harris Hip Score*:

The Harris score (HHS) is one of the main functional clinical scores used after hip replacement surgery and evaluates 3 "items" relating to the diseased or operated hip:

- Pain (44 points)
- Function (47 points)
- Mobility (9 points)

For a maximum total score of 100 (minimum score:0), the HHS results will be categorized as follows:

 Harris WH. Traumatic arthritis of the hip after dislocation and acetabular fractures: treatment by mold arthroplasty. An end-result study using a new method of result evaluation. *J Bone Joint Surg Am.* 1969; 51: 737–55.

HHS	
Excellent	90-100
Good	80-89
Correct	70-79
Bad	< 70

The HHS fill grid is available in **Appendix 5**.

- *Forgotten Hip Score (FJS-12):*

The Forgotten Hip Score (SHO-12) is the French version of the FJS-12 (*Forgotten Joint Score*). The objective of this self-questionnaire is to estimate the degree of neglect of the hip and knee prosthesis through 12 questions.

Each item has 5 levels of response:      Never: 0 points

Almost never: 1 point  
Rarely: 2 points  
Sometimes: 3 points  
Often: 4 points

The sum of the items is divided by the number of items and multiplied by 25 to obtain a score out of 100.

The OHSS Fill Grid is available in **Appendix 6**.

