### C. ANALYTICAL PROCEDURES

#### i. CALCULATION OF CONFIDENCE INTERVALS

All confidence intervals will be calculated at 95%, i.e.:  $z_{\frac{\alpha}{2}} = 1.96$

The confidence intervals for discrete qualitative and quantitative variables will be calculated using the following formula:

$$IC_{95} = \left[ p - z_{\frac{\alpha}{2}} \times \sqrt{\frac{p \times (1-p)}{n}} ; p + z_{\frac{\alpha}{2}} \times \sqrt{\frac{p \times (1-p)}{n}} \right]$$

With:

- $IC_{95}$ , the 95% confidence interval
- p, the proportion observed;
- $z_{\frac{\alpha}{2}} = 1.96$ , the value derived from the normal distribution for a risk  $\alpha$  5%;
- n, the sample size.

The confidence intervals for the means of the continuous quantitative variables will be calculated using the following formula:

$$IC_{95} = \left[ m - z_{\frac{\alpha}{2}} \times \frac{\sigma}{\sqrt{n}} ; m + z_{\frac{\alpha}{2}} \times \frac{\sigma}{\sqrt{n}} \right]$$

With:

- $IC_{95}$ , the 95% confidence interval
- $m$ , the observed mean;
- $\sigma$ , the standard deviation observed
- $z_{\frac{\alpha}{2}} = 1.96$ , the value derived from the normal distribution for a risk  $\alpha$  5%;
- $n$ , the sample size.

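### The optional mean/median imputation rule, if used with the plan's unadjusted interval formulas, makes secondary score intervals too narrow by about the missing fraction and can put all missing patients in one category

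*Protocol*

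**What the plan says.** Section 7.J.i, on missing data, states that "The simple imputation replacement method can be used if necessary" and describes it as an instruction to "replace the missing data with a plausible value (mean/median of the variable for the follow-up under consideration, for example"). The condition is "if less than 10% of the data are missing". The section does not say which variables it covers, or whether filled-in values enter the category tables.

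Section 7.C.i says "The confidence intervals for the means of the continuous quantitative variables will be calculated using the following formula": the mean plus or minus 1.96 times sigma over the square root of n. Sigma is defined there as "the standard deviation observed" and n as the sample size. Proportions get the matching normal-approximation interval. Neither formula separates observed from imputed values.

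Three other places show where these intervals and counts are used:
- Section 6.A.iii defines four HHS bands, into which "the HHS results will be categorized as follows", and a five-level satisfaction scale.
- Section 7.B, on pre- to postoperative score changes, says "The confidence interval of the observed differences will make it possible to quantify the improvement or deterioration of the clinical status".
- Section 7.J.ii makes sensitivity analyses optional.

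**The concern.** Filling gaps with the mean of the observed values adds nothing to the estimate, because the mean of the completed data is the mean of the observed data. The interval formula nevertheless treats the filled-in patients as measured. They have zero deviation from the mean, so sigma falls, and they are counted in n. Both effects shorten the interval.

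Median imputation has the same two effects. If the score is skewed, it also moves the mean.

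For a categorised result the effect is bias rather than false precision. One fill-in value belongs to one band, so every missing patient goes there and all other bands shrink.

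The study is descriptive, with no test and no success criterion (sections 7.D and 7.G). Its secondary output is these estimates and their 95% intervals. Because sensitivity analysis is optional, nothing in the plan would reveal the effect.

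**Working it through.** The plan states no figure of its own to reproduce here beyond z = 1.96 for 95%, which is correct (1.95996).

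**Inputs.** From the protocol: at most about 120 patients or stems (sections 6.C.viii and 7.E), fewer after deaths, refusals and losses; missing fraction strictly below 10% (7.J.i); the formulas of 7.C.i. Assumed: the 10% limit is read per variable, and values are missing completely at random. The totals below 120 are illustrative.

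**Mean score at one time point.** Let N be the number counted, k the number imputed at the observed mean, and r = N − k the number observed.
- Standard deviation ratio, imputed over observed: √[(r − 1)/(N − 1)].
- Interval width ratio: w = √[(r − 1)/(N − 1)] × √(r/N), which is close to 1 − k/N.
- Coverage: 2Φ(1.96 w) − 1.

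| N | imputed k | missing | w | too narrow by | coverage |
|---|---|---|---|---|---|
| 120 | 2 | 1.7% | 0.983 | 1.7% | 94.6% |
| 120 | 6 | 5.0% | 0.950 | 5.0% | 93.7% |
| 120 | 11 | 9.2% | 0.908 | 9.2% | 92.5% |
| 84 | 8 | 9.5% | 0.904 | 9.6% | 92.4% |
| 111 | 11 | 9.9% | 0.900 | 10.0% | 92.2% |
| 60 | 5 | 8.3% | 0.916 | 8.4% | 92.7% |

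Worked row, N = 120 and k = 11: √(108/119) × √(109/120) = 0.9527 × 0.9531 = 0.908.

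A simulation of 20,000 data sets for that row (normal scores, assumed mean 80 and SD 15) gave 92.2% coverage after imputation and 94.7% using the 109 observed values.

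**HHS change, only the follow-up value imputed.** Assume equal variance at both times (set to 1) and correlation ρ. An observed pair contributes variance 2(1 − ρ). A pair with an imputed follow-up contributes only the baseline variance, 1. With N = 120, k = 11 and r = 109, the width relative to the observed-pairs interval is

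√{ [(109 × 2(1 − ρ) + 11)/120]/120 ÷ [2(1 − ρ)/109] }.

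- ρ = 0: 0.931 (6.9% narrower)
- ρ = 0.3: 0.941 (6.0%)
- ρ = 0.5: 0.953 (4.7%)
- ρ = 0.7: 0.982 (1.8%)

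If the change itself is imputed, the single-time-point result applies, 9.2% here. SHO-12 has no change score to distort: the schedule in section 6.A.iv excludes it preoperatively.

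**Categories.** Suppose a share p of the observed patients lies in the band containing the fill-in value. After imputation the share is (p × r + k)/N.
- p = 30%, N = 120, k = 11: (32.7 + 11)/120 = 36.4%.
- p = 30%, N = 84, k = 8: (22.8 + 8)/84 = 36.7%.
- p = 20% and 40%, N = 120, k = 11: 27.3% and 45.5%.

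Every other band is multiplied by 109/120 = 0.908. At p = 30% and 109 observed, the interval half-width is 1.96 × √(0.30 × 0.70/109) = 8.6 points, so the 6.4-point shift is about three quarters of it.

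**The case against.** The strongest reply is that the rule is an option with an example attached. A reader might infer that the plan makes its score intervals 10% too narrow. The documents do not support that: nothing happens if the option is not used, and 10% is the limit that the strict ceiling approaches, not a typical value.

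The reach is also narrow. Patients are included at the same visit at which HHS, SHO-12 and satisfaction are collected (sections 6.C.v and 6.D.i), so few included patients should lack those values. The likelier gap is preoperative HHS from the records. If that gap reaches 10%, the rule switches itself off.

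A reader might also infer that the main result is affected. It is not: section 7.C.iii handles lost, deceased and withdrawn subjects by censoring.

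The category effect is partly inference. Section 7.J.i neither says that satisfaction is imputed nor that filled-in HHS totals are sorted into bands, and it does not say whether items or totals are meant. Filling single items would have a different, smaller effect.

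These points limit the size and scope of the concern, but do not remove it. The protocol itself names the method, so this is not detail left to a later document. Where the rule does apply, it gives a worse interval than the observed data alone and no better estimate. No section confines it to continuous variables or keeps imputed values out of n.

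**Conclusion.** The point holds as a conditional fault in a secondary analysis. If the option is used with the mean, intervals for mean HHS and SHO-12 are too narrow by about the missing fraction: 5% at 5% missing and up to 9 to 10% at the ceiling, with coverage about 92 to 92.5% instead of 95%. HHS change intervals are about 2 to 7% narrower than the observed-pairs interval if only the follow-up value is filled in. If imputed values are counted in bands or satisfaction levels, an assumed 30% share rises to about 36 to 37%.

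The interval figures rest on mean imputation and on data missing completely at random. The change-score range also rests on equal variances and on assumed correlations from 0 to 0.7, and the category figures on the assumed observed share. The width formula does not carry over exactly to the median, which would also shift the mean of a skewed score. No study decision turns on this, but the change is worth making because it costs almost nothing.

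**What to change.** Replace the rule in section 7.J.i with the following:
- Analyse the observed values of each variable.
- Use the number observed as n in the formulas of section 7.C.i.
- Report the number missing beside each result.
- Do not impute satisfaction or any categorised outcome.
- Multiple imputation, with its between-imputation variance carried into the interval, may be kept as an optional sensitivity analysis for score means or HHS change. It is not needed for the main tables.

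The cost is one paragraph of wording and less work than the present rule. Intervals will be wider than the rule would have given, by about 10 to 11% at the ceiling (1/0.908 = 1.10; 1/0.900 = 1.11) and about 5% at 5% missing. That extra width is the uncertainty that the imputation would have hidden.
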